- To evaluate if two novel treatment modalities (explained more briefly on page 9 in paragraph 'Study Onset' of chapter 'Methodology') show non-inferiority on subjective evaluations (symptom score on a Visual Analogue Scale (VAS), Therapeutic Response Evaluation (TRE) and Rhinitis Quality of Life Questionnaire (RQLQ)) compared to the current treatment modality of capsaicin nasal treatment in patients with IR. The gathered data of this single center trial can be used to guide the decision on the set-up and the design of a larger multi-center trial being powered to prove non-inferiority.

Our secondary aims are:

- To evaluate if the two novel treatment modalities show non-inferiority compared to the current treatment modality of capsaicin nasal treatment in patients with IR on objective evaluations (Peak Nasal Inspiratory Flow (PNIF) measurements before and after CDA challenge).
- To evaluate the occurrence of adverse events at week 4, week 12 and week 26 and recurrence of symptoms and NHR at week 26 in the different treatment groups.

B. Hypothesis

Non-inferiority in efficacy of the two novel treatment regimes i.e. capsaicin nasal spray 0,01mM (2puffs/nostril/day) during 4 weeks and capsaicin nasal spray 0,001mM (2puffs/nostril/day) during 4 weeks compared to the current treatment of capsaicin nasal spray 0,1mM (5/day administered on a single day) with regard to the scores on week 4 (taking into account the baseline level).

C. Outcome

- VAS for major nasal symptom at week 4, week 12 and week 26. The region of equivalence is defined as a difference in VAS of less than 1.
- VAS for total and individual nasal symptoms at week 4, week 12 and week 26. The region of equivalence is defined as a difference in VAS of less than 1.
- TRE (based on a scale from 1 to 5) at week 4, week 12 and week 26. The region of equivalence is defined as a difference in percentage for patients of less than 10% in all different TRE scoring groups.

- NHR (objectively measured by PNIF before and after CDA challenge) in all treatment modalities at week 4, week 12 and week 26. The region of equivalence is defined as a drop in PNIF of less than 10%.
- Appearance of adverse events at week 4, week 12 and week 26.
- Recurrence of symptoms (based on a scale of 1 to 5) at week 26.

Study design

A. Type of study

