The current study is not designed to prove non-inferiority, but serves as a pilot study to evaluate if non-inferiority is observed for the two novel treatment regimes compared to the current treatment regime. As many as possible IR patients matching the inclusion criteria (see above) will be recruited during the recruitment period. Based on previous experience in the center, the expected total number of IR patients equals 120 taking into account a recruitment period of three years. If it is possible to include 120 patients before the time frame of three years has finished, recruitment will be stopped earlier. If by any unforeseen circumstances, after three years still not enough patients are included in the study, recruitment will be running until a total number of 120 patients will be obtained.

Note:

A drop out rate of 10% due to concomitant infection, loss of follow-up or non-related adverse events is possible during the setting.

D. Statistics

A linear model for longitudinal measures (More specifically, a direct likelihood approach is adopted using an unstructured covariance matrix (Molenberghs and Kenward, 2007, Section 14.4)¹) will be used to compare the evolution of VAS, RQLQ and drop in PNIF between the four groups, with the baseline value as a covariate. A transformation of the outcome will be considered when needed to handle skewness in the distribution of the model residuals. Differences between the groups will be compared with the a-priori defined regions of equivalence (see section Outcomes). 95% confidence intervals for differences at specific time points will be reported. Note again that the aim of this pilot study is to describe the pattern of the differences, and not to prove non-inferiority based on these confidence intervals. For the evaluation of the TRE, a

¹ G. Molenberghs and M.G. Kenward. Missing Data in Clinical Studies. Hoboken, NJ : John Wiley & Sons, 2007.

logistic regression model using generalized estimating equations (GEE)² will be used to compare the evolution in proportion patients free of complaints (TRE score 5), with the baseline TRE score as covariate.

E. Patient recruitment

Patients will be enrolled by four different strategies:

- Patients with a new diagnosis of IR who visit the ENT department at the University Hospital of Leuven will be offered the possibility to take part in this study and will be screened for in- and exclusion criteria.

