As this study will include four parallel arms of equal sample size, the 120 included IR patients will be randomized in four equal groups of each 30 patients (n=30 patients per treatment arm). A block randomization with varying block sizes will be used.

G. Demographic and clinical information

Patient's demographic information as well as general medical history will be gathered from medical records and verified during the screening visit to the Outpatient clinic.

Demographic data of importance are: age, gender, smoking, occupation, exposure to agents during professional or recreational activity, concomitant bronchial disease (asthma, COPD), aspirin intolerance and current medication use.

The respective information is gathered in case report forms (CRFs) and will be analyzed by GraphPad Prism 6.

H. Time schedule and visit table

[figure not shown]

Table 2: Schematic visualization of the timeframe and visit table

As demonstrated in table 1, the included patients will visit the ENT Department of UZ Leuven at six occasions.

- Screening visit (week -3)

Explanation of study, study protocol and treatment.

Inclusion in study after signing the informed consent form.

Evaluation of inclusion and exclusion criteria.

Pregnancy test for women with childbearing potential.

Skin prick test for common aero-allergens if not yet performed.

Blood tests for total and/or specific IgE.

Nasal endoscopy for exclusion of anatomic deformities, rhinosinusitis or nasal polyps.

Symptom evaluation using VAS scores for individual and total nasal symptoms.

Quality of life evaluation using the rhinitis quality of life questionnaire (RQLQ).

- Baseline visit (week -1):

Re-evaluation of the inclusion and exclusion criteria.

Clinical nasal examination including nasal endoscopy.

NHR challenge (by CDA provocation and/or hyperosmolar discs).

Nasal fluid collection before and after NHR challenge.

Evaluation of nasal airflow by peak nasal inspiratory flow (PNIF) device before and after NHR provocation.

Symptom evaluation using VAS scores for individual and total nasal symptoms.

Quality of life evaluation using the rhinitis quality of life questionnaire (RQLQ).

- Randomization and start of treatment (week 0):

Explanation treatment i.e. five applications of capsaicin/placebo nasal spray with a one-hour interval, followed by handing over the capsaicin nasal spray or placebo for the following four weeks.

Brief nasal examination.

Evaluation of adverse events.

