Two weeks after treatment, patients will be contacted by telephone in order to evaluate adverse events, check adherence and evaluate therapeutic response.

- Follow-up visit 1 (week 4):

Nasal examination including nasal endoscopy.

NHR measurements by CDA and/or hyperosmolar discs.

Nasal fluid collection by Merocell (both nostrils) for measurement of neuromediators before and after NHR measurements.

Measurement of PNIF before and after NHR measurements.

Evaluation of the therapeutic response (TRE) on a scale from 1 (= no relief of symptoms) to 5 (= total relief of symptoms).

Symptom evaluation (VAS) for INS and TNS.

Quality of life evaluation using the RQLQ.

Evaluation of adverse events and check of adherence.

- Follow-up visit 2 (week 12):

Identical to FU 1

- Follow-up visit 3 (week 26):

Nasal examination including nasal endoscopy.

Evaluation of the therapeutic response (TRE) on a scale from 1 (= no relief of symptoms) to 5 (= total relief of symptoms).

Symptom evaluation (VAS) for INS and TNS.

Quality of life evaluation using the RQLQ.

Evaluation of adverse events and check of adherence.

	Screening week -3	Baseline week -1	Treatment week 0	FU visit 1 week 4	FU visit 2 week 12	FU visit 3 week 26
Explanation study and protocol	x					
Informed consent	x					
Evaluation in-and exclusion criteria	x	x				
Pregnancy test (if necessary)	x					
SPT (if necessary)	x					
Blood analysis	x					
ENT exam with nasal endoscopy	x	x	x	x	x	x
Nasal fluid collection		x/x*		x/x*	x/x*	
Explanation R/	x		x			
Start R/, handing over study medication and diary			x			
NHR measurements		x		x	x	
TRE				x	x	x
Symptom evaluation VAS	x	x		x	x	x
Symptom evaluation RQLQ	x	x		x	x	x
AEE and check adherence			x	x	x	x

ENT: ear, nose, throat

TRE: therapeutic Response Evaluation

AEE: Adverse Events Evaluation

*: x/x = before and after NHR measurements

Table 3: Overview of registrations and sample collections that were performed at each visit

I. Variables

- Clinical ENT exam:

Nasal endoscopy will be performed by an experienced MD.

- Skin Prick Test (SPT):

SPT for the 18 most prevalent inhalant allergens (e.g. house dust mite, grass, mugwort, alder, birch, hazel, pet animals, Alternaria, Aspergillus) provided by HAL Allergy, will be performed by investigators Apr. [name] or CTA [name].

- Blood analysis:

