Functional problems that are most troublesome to adults with rhinitis will be measured by the RQLQ by 28 questions in 7 domains (activity limitation, sleep problems, nose symptoms, eye symptoms, non-nose/eye symptoms, practical problems and emotional function). There are three 'patient-specific' questions in the activity domain, which allow patients to select three activities in which they are most limited by their rhinitis. Patients recall how bothered they have been by their rhinitis during the previous week and to respond to each question on a 7-point scale (0 = not impaired at all and 6 = severely impaired). The overall RQLQ score is the mean of all 28 responses and the individual domain scores are the means of the items in those domains. The RQLQ has excellent measurement properties and has been used extensively throughout the world both in clinical practice and clinical trials. The validation studies have shown that these properties are very similar to

those found for the Asthma Quality of Life Questionnaire (21). Patients will be asked to score RQLQ before treatment and at week 4, 12 and 26.

- Adherence evaluation:

Patients will be asked to bring their nasal spray with them on follow up visit 2 at week 4. Weighing the residual fluid on day 28 will objectively check adherence.

All patients will be asked to write down their symptoms, adverse events and degree of sensitization/desensitization in a dairy (see addendum). The diary will be handed over to them at the day of the treatment.

- Therapeutic Response Evaluation (TRE):

TRE will be measured on a 1 to 5 scale.

- 5 klachten zijn volledig verdwenen = klachtnvrij
- 4 klachten zijn bijna volledig verdwenen
- 3 klachten zijn verminderd, doch nog aanwezig
- 2 klachten zijn licht verminderd, doch nog sterk aanwezig
- 1 klachten zijn onveranderd ten opzichte van vóór de behandeling

Patients will be asked to score their symptom relief on week 4, week 12 and week 26.

- Evaluation of recurrence of symptoms:

The recurrence of symptoms will be measured on a 1 to 5 scale.

- 5 klachten zijn volledig terug aanwezig
- 4 klachten zijn voor een aanzienlijk deel terug aanwezig
- 3 klachten zijn nog steeds duidelijk verminderd
- 2 klachten zijn licht verminderd, doch beginnen terug te keren
- 1 klachten zijn nog steeds volledig verdwenen

Patients will be asked to score their recurrence of symptoms at week 26.

References

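### The TRE model adjusts for a baseline TRE score that is never collected and that the scale cannot supply

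*Combined protocol and SAP*

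**What the plan says.** In Methodology, D. Statistics, the TRE analysis is a logistic regression fitted by GEE, used to "compare the evolution in proportion patients free of complaints (TRE score 5), with the baseline TRE score as covariate". The same section adjusts the longitudinal models for VAS, RQLQ and drop in PNIF for their own baseline values.

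TRE belongs to the primary aim. Objectives, A. Aims names it among the subjective evaluations: "Therapeutic Response Evaluation (TRE) and Rhinitis Quality of Life Questionnaire (RQLQ"), alongside the VAS symptom score. Objectives, B. Hypothesis frames the comparison "with regard to the scores on week 4 (taking into account the baseline level").

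The statements on when TRE is measured agree with one another:

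- Objectives, C. Outcome: "TRE (based on a scale from 1 to 5) at week 4, week 12 and week 26".
- Methodology, I. Variables: "Patients will be asked to score their symptom relief on week 4, week 12 and week 26".
- Methodology, H. Time schedule: the follow-up visits list "Evaluation of the therapeutic response (TRE) on a scale from 1 (= no relief of symptoms) to 5 (= total relief of symptoms"). The week -1 baseline visit lists "Symptom evaluation using VAS scores for individual and total nasal symptoms" and the RQLQ, but no TRE.

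The lowest level of the scale, score 1, reads "klachten zijn onveranderd ten opzichte van vóór de behandeling", that is, complaints unchanged compared with before treatment.

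**The concern.** A covariate must be measured, and must vary between patients, before a model can adjust for it. A baseline TRE meets neither condition. This is more than a box left unticked in the visit table: the scale rates relief since treatment, so the pre-treatment state is its reference point, and adding a baseline TRE assessment would not supply a usable covariate.

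For TRE, this covariate is the only means the plan gives of taking the baseline level into account. The analyst will have to improvise, and the available choices are not equivalent:

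- Dropping the term gives an unadjusted comparison, which is valid but is not the stated analysis.
- Substituting another baseline measure changes the odds ratio being estimated, because adjusted and unadjusted logistic odds ratios generally differ even under randomisation.
- Treating the first recorded TRE (week 4) as the baseline would condition on a post-treatment outcome at the very time point the hypothesis addresses. The plan does not propose this, but its wording does not exclude it.

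The choice should be fixed before anyone can see results by arm.

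**Working it through.** The plan gives no figure to reproduce here. The check compares the measurement schedule with the model and then examines whether the model can be estimated.

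**Inputs.** 120 patients in four arms of 30 (Methodology, A. Study onset). Three TRE visits, at weeks 4, 12 and 26 (Outcome; Variables; Table 3). Possible drop-out of 10% (Methodology, C. Sample size and setting).

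**Step 1: the schedule, from Table 3 and the visit lists.**

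| Measure | Week -3 | Week -1 | Week 0 | Week 4 | Week 12 | Week 26 |
|---|---|---|---|---|---|---|
| VAS | x | x | | x | x | x |
| RQLQ | x | x | | x | x | x |
| TRE | | | | x | x | x |

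TRE is scheduled at 0 of the 3 visits up to and including week 0, and at 3 of the 3 visits afterwards. The only other contact that evaluates therapeutic response is a telephone call two weeks after treatment, which is also post-randomisation. VAS and RQLQ do have pre-treatment values, so the gap is specific to TRE.

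**Step 2: baseline TRE treated as missing.** Planned TRE records: 120 × 3 = 360. Records with an observed baseline TRE: 0. A complete-case fit keeps 0 of 360 records and stops with an error. Drop-out changes the denominator only. With 10% × 120 = 12 drop-outs:

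- all leaving before week 4: 108 × 3 = 324 records;
- all leaving between weeks 12 and 26: 120 + 120 + 108 = 348 records.

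The plan does not say when drop-outs leave, so the total lies between 324 and 348. The number with a baseline TRE is 0 throughout.

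**Step 3: baseline TRE set to 1 for everyone (unchanged).** Write the model for patient *i* in arm *g* at visit *j* as

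logit P(TRE = 5) = μ(g, j) + γ × B(i),

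with 4 × 3 = 12 arm-by-visit means μ. If B(i) = 1 for every patient, the right-hand side is μ(g, j) + γ. Only that sum can be estimated; γ cannot be separated from the level of the means.

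| Design matrix (360 rows) | Columns | Rank |
|---|---|---|
| Arm by visit | 12 | 12 |
| Plus baseline TRE = 1 | 13 | 12 |
| Plus a covariate that varies between patients (illustrative baseline VAS, drawn from 5 to 10) | 13 | 13 |

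A GEE fit with exchangeable correlation to invented data (120 patients, 4 arms, 3 visits) showed the same thing. Adding the constant only split the intercept, -1.386 into -0.693 and -0.693. All arm and visit log odds ratios and their standard errors agreed to below 1e-14. The response rates and the working correlation were invented for illustration; the rank result depends on neither.

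**Step 4: a covariate that can be used.** The last row of the table shows that a measure varying between patients makes the adjusted model estimable. The week -1 VAS for total nasal symptoms is such a measure and is already scheduled.

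**The case against.** The strongest reply is that little harm follows. The trial is described as a pilot that is to describe the pattern of differences, not to prove non-inferiority. Randomisation makes the unadjusted TRE comparison valid, and setting the covariate to 1 leaves every arm effect unchanged. A fit on an entirely missing covariate fails visibly, so it cannot yield a wrong result unnoticed. All of this stands, and it limits the seriousness of the point. It does not make an unworkable specification acceptable in a trial whose results are meant to guide the design of a larger one.

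A second reply is that TRE is itself a rating of change, so the pre-treatment state is already built into the outcome. That is fair as far as it goes. But the plan asks for a baseline covariate in addition, and the one it names cannot provide it.

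A third reply is that the choice of replacement is a matter of judgement. The documents do not show that baseline VAS predicts a TRE score of 5. Entry requires a total nasal symptom score of at least 5, which narrows its range. An adjusted odds ratio is not the unadjusted one, and few patients per arm may reach score 5. This also stands: the contradiction by itself compels only deletion of the clause. A further mismatch, between an odds ratio and a TRE equivalence region stated as a percentage difference, is already present in the plan's logistic model and is not created by the replacement.

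None of these replies identifies a baseline TRE. Some figures and the diary addendum were not available, but Table 3 is legible and agrees with the text, and the diary is handed out only on the treatment day.

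**Conclusion.** The concern holds and should be fixed. As written, the TRE model cannot be run with its stated adjustment: the covariate exists for 0 of 120 patients on the planned schedule, or is constant and uninformative if imputed as 1. The consequence is an unspecified departure from the plan for one of three measures in the primary aim. Bias in the randomised comparison is not shown, and the VAS and RQLQ models are unaffected. The conclusion rests on the schedule and scale definition in the current text, and on the assumption that no pre-treatment TRE is recorded in material that was not available. It does not depend on any response rate, correlation or drop-out pattern.

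**What to change.** Before unblinding, replace the covariate clause of the TRE sentence in Methodology, D. Statistics with wording such as:

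> *adjusted for the week -1 VAS for total nasal symptoms; no TRE value obtained after randomisation enters the model as a covariate.*

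This VAS is collected before randomisation and, like TRE, rates complaints overall. It is also recorded at week -3, so the visit must be named. Baseline RQLQ would serve as well. If the sponsor prefers not to adjust, the minimum correction is to delete the clause and state that the TRE comparison has no baseline covariate.

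The cost is one sentence. No new data, visits or patients are needed.

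### The TRE model adjusts for a baseline TRE score that is never collected, and the TRE region is undirected and spans five score groups while the model covers only score 5

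*Combined protocol and SAP*

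**What the plan says.** TRE is one of three instruments in the primary aim (Objectives, A. Aims), with the VAS and the RQLQ. The hypothesis is "Non-inferiority in efficacy of the two novel treatment regimes" against the current regimen, "with regard to the scores on week 4 (taking into account the baseline level" (Objectives, B. Hypothesis).

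For TRE the Outcome section states: "The region of equivalence is defined as a difference in percentage for patients of less than 10% in all different TRE scoring groups". It gives no direction and does not say whether 10% is absolute or relative.

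Methodology, D. Statistics, says: "Differences between the groups will be compared with the a-priori defined regions of equivalence (see section Outcomes". The only TRE model it names is a logistic GEE to "compare the evolution in proportion patients free of complaints (TRE score 5), with the baseline TRE score as covariate". It also says that "the aim of this pilot study is to describe the pattern of the differences, and not to prove non-inferiority" from the confidence intervals.

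Table 3 marks TRE at the week 4, 12 and 26 visits only, and the TRE entry under I. Variables gives the same three times. The scale runs from 1 (complaints unchanged from before treatment) to 5 (complaint-free).

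**The concern.** Two things do not fit together.

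- **Covariate.** The model needs a variable that the schedule does not supply and that the scale cannot supply, because TRE is itself a rating of change from the pre-treatment state.
- **Benchmark and model.** The benchmark is two-sided over five categories, the hypothesis is one-sided, and the model covers one category. The plan does not say how the model output is to be set against the benchmark, or which direction of difference is unfavourable in each score group.

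These choices would be made after the data are seen, for an instrument in the primary aim whose results are meant to guide the design of a larger trial.

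**Working it through.** **Inputs.** Five TRE categories, a 10% region, 30 patients per arm (A. Study onset) and possible dropout of 10% (C. Sample size and setting), which leaves 30 × 0.9 = 27. The documents give no TRE distribution, so every TRE rate below is an assumption. The sample size of 120 comes from expected recruitment; there is no power calculation to reproduce, and 4 × 30 = 120 agrees.

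**1. Is a baseline TRE collected?** The screening, baseline and week 0 visit lists contain no TRE, and Table 3 agrees. One other contact touches therapeutic response: "Two weeks after treatment, patients will be contacted by telephone in order to evaluate adverse events, check adherence and evaluate therapeutic response". It follows treatment and cannot serve as a baseline.

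**2. Could one be filled in?** On this scale the only possible pre-treatment value is 1 for everyone. A design matrix with an intercept, three arm terms and that constant has 5 columns and rank 4. The constant duplicates the intercept, so its coefficient cannot be estimated. Adding time and arm-by-time terms does not change this.

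**3. Direction.** Let d_k be the new minus current proportion in score k. The region requires |d_k| < 0.10 for all k. Take an assumed current regimen with 20% in each score and a new regimen with 10/15/20/20/35% (scores 1 to 5). The differences are −10, −5, 0, 0 and +15 points. The new regimen is better and lies outside the region. Because the five differences sum to zero, any real shift raises some shares and lowers others, so no single sign means worse in all five groups.

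**4. One category against five.** Take an assumed current regimen of 10/10/20/40/20% and a new one of 50/10/10/10/20%. The differences are +40, 0, −10, −30 and 0 points. Score 5 is 20% in both, so the score-5 model shows no difference (odds ratio 1) although far more patients are unchanged.

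**5. Scale.** The odds ratio for a 10-point fall from current rate p is [(p − 0.10)/(1.10 − p)] / [p/(1 − p)].

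| Current rate | Odds ratio |
|---|---|
| 20% | (0.10/0.90)/(0.20/0.80) = 0.44 |
| 30% | (0.20/0.80)/(0.30/0.70) = 0.58 |
| 40% | (0.30/0.70)/(0.40/0.60) = 0.64 |
| 50% | (0.40/0.60)/(0.50/0.50) = 0.67 |

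No single odds ratio stands for the region, so the conversion to a risk difference has to be specified.

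**6. Precision of a score-5 risk difference.** The 95% half-width is 1.96 × √(2p(1 − p)/n).

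| Rate p | n = 30 | n = 27 |
|---|---|---|
| 10% | 15.2 points | 16.0 points |
| 20% | 20.2 | 21.3 |
| 30% | 23.2 | 24.4 |
| 50% | 25.3 | 26.7 |

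All exceed 10 points, so the result can only be descriptive, as the plan says.

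**7. What an ordinal summary adds.** Let θ be the probability that a patient on the new regimen scores higher than one on the current regimen, ties counted as half; 0.50 means no difference. For the example in step 4, summing over the new regimen's scores 1 to 5:

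θ = 0.50(0.05) + 0.10(0.15) + 0.10(0.30) + 0.10(0.60) + 0.20(0.90) = 0.31.

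In simulation at 30 per arm, the estimate falls below 0.50 in over 99% of trials and the whole 95% interval in about 74%. For the better regimen in step 3, θ = 0.61. The interval half-width runs from about 0.12 (70% of patients in one score) to 0.14 (uniform).

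**The case against.** - **The covariate is a one-phrase slip.** A constant drops out, and what remains is a valid comparison of randomised arms; TRE already refers to the pre-treatment state. This largely stands. Deleting the phrase alone would make the model fittable, and baseline VAS is a sensible replacement, not a necessary one. The model as written still cannot be fitted, and the hypothesis's baseline adjustment is not met through this covariate.
- **The plan speaks of a proportion, not odds.** This stands. A logistic GEE can return proportions and a risk difference, so a reader who infers from step 5 that model and region cannot be compared goes too far. The conversion is an unspecified step, not an error.
- **The region is descriptive and the VAS regions are undirected too.** The first part stands and limits the consequence. The second is true, but a single VAS difference has an obvious unfavourable side, whereas five shares that sum to 100% have no common one.
- **The all-five rule rejects identical arms.** A reader might infer this from simulation, but the plan states no joint pass/fail rule on observed differences. Under that one reading at 30 per arm, identical arms fall inside in about 10% of trials (uniform), 28% (70/10/10/5/5%), 34% (70/20/10/0/0%) or 52% (70/30/0/0/0%). Taken one category at a time, the figure is 48% at a share of 50%, 73% at 10% and 87% at 5%. If the region refers to true differences, identical arms are inside. These figures depend on the reading and the assumed distribution and are not a property of the plan.
- **Narrowing the benchmark to score 5 would lose scope.** This stands. With a score-5 rule alone (not worse by 10 points or more), the step 4 regimen would pass in about 79% of trials at 30 per arm. The repair should keep all five groups in view.

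**Conclusion.** The baseline TRE covariate is wrong as written: it is not collected, and on this scale it would be undefined or constant. This rests on the protocol text alone. The TRE region also does not match its hypothesis or its model: it is undirected under a non-inferiority hypothesis, so a gain of 10 or more points in score 5 lies outside it, and scores 1 to 4 have no planned model estimate. That reading takes 10% as percentage points, which the protocol does not state.

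A reader might infer that the trial would reach a wrong non-inferiority conclusion on TRE. The documents do not support that, because the study disclaims proof of non-inferiority and attaches no decision to the region. The consequence is an ambiguous TRE analysis feeding the next trial's design. It should be fixed, at small cost.

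**What to change.** 1. Delete the baseline TRE score from the model and adjust for the VAS total nasal symptom score from the baseline visit (week −1), where the schedule already has "Symptom evaluation using VAS scores for individual and total nasal symptoms".
2. Report the week-4 score-5 comparison from the GEE as a standardised risk difference (new minus current regimen) with a 95% CI. State that only a lower proportion with score 5 is unfavourable. State that 10% means percentage points, which the sponsor should confirm. If an arm has no patient with score 5, report the raw difference with a Newcombe interval; at an assumed true rate of 5% this happens in 0.95^30 = 21% of arms of 30.
3. Keep the five-group scope. Tabulate all five category differences with 95% CIs and add θ with its 95% CI, so that a gain in score 5 is not read as a breach and worsening among scores 1 to 4 remains visible.

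**Cost.** Edits to one outcome bullet and the TRE model sentence, plus one added table and summary; no new data, visits or patients. The estimates remain imprecise: on point estimates, a regimen truly 10 points worse would still look less than 10 points worse in about 43 to 45% of trials at 30 per arm (assumed current rates 20 to 50%). The ordinal summary has no margin in the protocol and must be read as description.
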